#### **13.2 Definition of a Serious Adverse Event (SAE)**

A serious adverse event is any AE that:

- a) results in death
- b) is life threatening

*Note: The term 'life-threatening' in the definition of 'serious' refers to an event in which the participant was at risk of death at the time of the event. It does not refer to an event, which hypothetically might have caused death if it were more severe.*

- c) requires hospitalisation or prolongation of an existing hospitalisation.

*Note: In general, hospitalisation signifies that the participant has been detained (usually involving at least an overnight stay) at the hospital or emergency ward for observation and/or treatment that would not have been appropriate in the physician's office or out-patient setting. Complications that occur during hospitalisation are AEs. If a complication prolongs hospitalisation or fulfils any other serious criteria, the event is serious. When in doubt as to whether 'hospitalisation' occurred or was necessary, the AE should be considered serious.*

*Hospitalisation for elective treatment of a pre-existing condition that did not worsen from baseline is not considered an AE.*

- d) results in disability/incapacity, or

*Note: The term disability means a substantial disruption of a person's ability to conduct normal life functions. This definition is not intended to include experiences of relatively minor medical significance such as uncomplicated headache, nausea, vomiting, diarrhoea, influenza, and accidental trauma (e.g. sprained ankle) which may interfere or prevent everyday life functions, but do not constitute a substantial disruption.*

e) is a congenital abnormality / birth defect.

Medical and scientific judgement should be exercised in deciding whether reporting is appropriate in other situations, such as important medical events that may not be immediately life-threatening or result in death or hospitalisation, but may jeopardise the participant or may require medical or surgical intervention to prevent one of the other outcomes listed in the above definition. These should also be considered serious. Examples of such events are invasive or malignant cancers, intensive treatment in an emergency room or at home for allergic bronchospasm, blood dyscrasias or convulsions that do not result in hospitalisation, or development of drug dependency or abuse.

The investigator will exercise his or her medical and scientific judgement in deciding whether an abnormal laboratory finding or other abnormal assessment is clinically significant.

### **13.3 Time Period, Frequency, and Method of Detecting AEs and SAEs**

All SAEs will be recorded from the time of consent until the final follow up visit at week 26.

Other adverse events possibly, probably, or definitely attributable to the intervention will be recorded from the time of consent until the final follow up visit at week 26.

Each participant will be monitored regularly by the site investigator and study personnel for events occurring throughout the study. During the period in hospital, the site investigator will enquire about AEs by asking the following non-leading questions:

*“How are you feeling?”*

At subsequent scheduled intervals participants will be asked:

*“Since you were last asked, have you felt unwell or different from usual?”*

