### **7.2 Inclusion and Exclusion Criteria**

Participants will be identified, recruited, and will participate in first assessment within 42 days of brain injury.

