electronic or digital signature or verbally. In the latter scenario the baseline assessor will read aloud information from the Participant Information and Consent Form to provide the patient with project information. The patient's verbal decision will be recorded in the CRF at the recruiting hospital. The patient will then be sent a copy of the study's information sheet. In the case of the investigator not having had the opportunity to approach the person whilst in hospital, the investigator will telephone them, to see if they would be interested in hearing more about the project/being involved. If the person agrees for their name to be given to the clinical trial team, the baseline assessor will then see the person at their home, mutually agreed location or will contact via telephone/telehealth facility in order to further discuss the project, obtain informed consent, and complete the baseline assessment and processes will proceed as above. The informed consent process will involve the use of 'aphasia friendly' information to accommodate patients with communication disorders, those with other cognitive issues typically associated with brain injury, and those with limited literacy skills. The process will also involve a relevant interpreter as needed. In the case of patients with a decision making disability who are incapable of providing consent, we will apply a Research Decision Maker consent pathway. Within this study, exclusion on the basis of inability to give consent would discriminate against individuals with severe brain injury, as the intervention provides additional client and family support and monitoring, rather than being a specific activity based or pharmaceutical intervention.

Participants can be recruited to the study at any time within six weeks post injury.

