## **10.4 Service data**

Site data will be collected with respect to services delivered to each participant for six months during the control and intervention periods. This data will consist of:

- Occasions of service per allied health discipline (Physiotherapy, Occupational Therapy, Speech Pathology, Social Work, Dietetics; Clinical Psychology/ Neuropsychology; Prosthetics/Orthotics; Therapy Assistant; inpatient and outpatient)

The data will be collected through a medical file review process and through access to hospital administrative data systems as needed.

In addition, *Minimum Process of Care Indicators* will capture data on whether key processes of care occurred while the patient was in hospital and/or within 26 weeks of injury.

The data collection will:

- involve extraction of relevant data from medical file (audit process)
- be undertaken by an independent blinded auditor
- include hospital sites at which patients were admitted for the index admission and any related contiguous admission or related admission
- will include inpatient and hospital notes
- be audited cumulatively i.e. they will be checked for occurrence across the 26 week follow up period
- note the timing of items with reference to the index admission will be recorded
- occur at 6 month intervals

The Minimum Processes of Care are the following:

- patient assessed by allied health within 48 hours of admission
- Aboriginal Liaison Officer involved during inpatient stay
- language noted in medical file
- interpreter used if Aboriginal language is participant’s primary language
- telephone or face to face contact with family made by any allied health staff during inpatient stay
- Aboriginal brain injury educational resource provided during inpatient stay
- inpatient allied health service provided (any discipline)
- discharge plan developed with patient and family at family conference

- outpatient allied health service provided (any discipline)

In the case of participants returning from a metropolitan hospital to a regional/rural/remote location:

- verbal contact made by the metropolitan hospital with local rural service provider (hospital and local Aboriginal Medical Service)
- discharge report from metropolitan hospital sent to rural service provider (hospital and local Aboriginal Medical Service)

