### *1. Safety*

Adverse events are expected to have a Poisson or negative binomial distribution. The distribution will be examined and the appropriate regression models will be used to compare counts of serious adverse events between conditions. Logistic regression will be used to compare binary adverse events (e.g. death). Risk ratios will be adjusted as per primary analysis with age, and mRS included as covariates.

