### *5. Interim analyses*

The DSMC will review interim data for adverse events and serious adverse events. The DSMC will use the Haybittle-Peto boundary with a difference of at least 3 standard errors in the analysis of serious adverse events (e.g. death

from all causes, aspiration pneumonia within the first 50 days post injury) needed to justify halting, or modifying the study before the planned completed recruitment. There will be no interim analyses for efficacy.

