**APPENDIX 1: Schedule of Assessments**

Assessment	Baseline Between Day 2 and Day 28 post injury	12 Weeks	26 Weeks
		Week 12 12 weeks post injury +/- 7 days	Week 26 26 weeks post injury +/- 14 days
Screening/Eligibility	X		
Consent	X		
Demographics	X		
Past medical History	X		
Brain injury subtypes	X		
NIHSS	X		
GCS	X		
mRS	X	X	X
FIM TM	X	X	X
Modified Caregiver Strain index		X	X
Hospital Anxiety and Depression Scale	X	X	X
EuroQol-5D-3L		X	X
Allied health OOS		X	X
Minimum processes of care		X	X
Resource Utilisation		X	X
Adverse Events		X	X
SAEs		X	X

X = Person screening the participant

X = Trained Baseline Assessor

X = Blinded Assessor

X = Blinded file auditor

X = Blinded data extractor

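### An example event for the DSMC stopping boundary is counted from injury, but SAEs are recorded only from consent, so 4% to 84% of its 50-day window is unobserved depending on the consent day

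*Protocol*

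**What the plan says.** Four places in the Protocol bear on this.

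- **Start of SAE recording (Section 13.3):** "All SAEs will be recorded from the time of consent until the final follow up visit at week 26". Section 10.6 uses the same consent start for attributable AEs and gives no earlier start for SAEs.
- **Interim rule (Section 16.4.2, item 5):** "The DSMC will use the Haybittle-Peto boundary with a difference of at least 3 standard errors", applied to serious adverse events. Two examples are given: death from all causes, and "aspiration pneumonia within the first 50 days post injury".
- **Latest consent:** Section 9 says "Participants can be recruited to the study at any time within six weeks post injury", and Section 7.2 says "Participants will be identified, recruited, and will participate in first assessment within 42 days of brain injury". Section 10.2.1 also uses 42 days. Appendix 1, whose first column includes consent, is headed "Baseline Between Day 2 and Day 28 post injury", and the table in Section 16.2 gives 0 to 4 weeks.
- **Final safety comparison (Section 16.4.2, item 1):** "the appropriate regression models will be used to compare counts of serious adverse events between conditions".

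The file audit in Section 10.4 will "include hospital sites at which patients were admitted for the index admission and any related contiguous admission or related admission", but it is set up to collect process-of-care indicators, not SAEs. Baseline collection covers medical history and comorbidities. No section asks anyone to look back for SAEs between injury and consent.

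**The concern.** A monitoring boundary is only as good as the counts fed into it. Here the event is defined over days 0 to 50 after injury, while the data start on whatever day the participant consents. An aspiration pneumonia during the index admission but before consent falls inside the event definition and outside the recording rule. Hospital staff who have had the cultural security training may already be treating the patient at that time, so such an event can occur under one component of the intervention. The coordinator component serves enrolled participants and is less affected.

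Two consequences follow. First, events are lost, so the DSMC has less information with which to see harm. Second, the number recorded depends on how quickly people are consented. Section 9 permits later consent by telephone or telehealth when a participant has been discharged or hospital restrictions prevent a visit, so lag may vary by site and over time. Under the design in Section 5 every site is in control in the first period and every site is in intervention in the last two. A lag that drifts with calendar time is therefore partly a lag that differs by condition.

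When SAE collection starts is a data-collection rule. A later analysis plan cannot recover events that were never recorded.

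**Working it through.** **Inputs.** Event window 50 days from injury (Section 16.4.2, item 5). Recording starts at consent (13.3). Latest consent is day 42 (7.2, 9, 10.2.1) or day 28 (Appendix 1). Earliest day in Appendix 1 is day 2. Boundary is 3 standard errors. The Protocol states no figure for the observed share or for the distribution of consent days, so there is none to reproduce.

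**Step 1: unobserved share.** For consent on day c, the share of the window before recording starts is c/50.

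| Consent day | Days observed | Share of window unobserved |
|---|---|---|
| 2 | 48 | 4% |
| 7 | 43 | 14% |
| 14 | 36 | 28% |
| 28 (Appendix 1 limit) | 22 | 56% |
| 42 (body text limit) | 8 | 84% |

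If consent days were uniform (an assumption), the mean unobserved share would be (2 + 28)/2/50 = 30% over days 2 to 28, and (2 + 42)/2/50 = 44% over days 2 to 42. If risk is higher early, the share of events missed exceeds the share of time missed. With a hazard that halves every 14 days (assumed), consent on day 14 misses 54.6% of events, not 28%.

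**Step 2: effect on the comparison.** Assume no intervention effect, a true 50-day risk of 10%, and 156 participants per condition (312/2). With p the observed risk in each condition and p̄ their mean, z = (p_int − p_ctl)/√(2p̄(1 − p̄)/156). Example, constant hazard, lag 7 days in control and 21 in intervention: p_ctl = 0.10 × 43/50 = 0.086, p_int = 0.10 × 29/50 = 0.058, ratio 0.67, z = −0.96.

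| Lag, control v intervention | Ratio, constant hazard | z | Ratio, 14-day half-life | z |
|---|---|---|---|---|
| 14 v 14 | 1.00 | 0.00 | 1.00 | 0.00 |
| 7 v 21 | 0.67 | −0.96 | 0.43 | −1.58 |
| 2 v 28 | 0.46 | −1.80 | 0.20 | −2.80 |
| 2 v 42 | 0.17 | −3.07 | 0.05 | −3.55 |

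At an assumed risk of 20%, 7 v 21 gives z of −1.41 or −2.30, and 2 v 28 gives −2.65 or −4.08. An interim look has fewer participants, which shrinks |z|.

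**Step 3: sensitivity to the lag model.** If everyone consented on exactly day 10 in one condition and exactly day 20 in the other, identical risks would give a recorded ratio of 30/40 = 0.75 under a constant hazard, or 0.132/0.367 = 0.36 under an assumed 7-day half-life. These two ratios hold only for fixed consent days. With consent spread uniformly over days 2 to 18 and 2 to 38 (the same means of 10 and 20), the 7-day half-life gives 0.218/0.407 = 0.54.

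**Step 4: does person-time repair it?** Take 7 v 21 days. Under a constant hazard, rates per person-day are 0.086/43 = 0.0020 and 0.058/29 = 0.0020, ratio 1.00, so the bias is removed. With the 14-day half-life they are 0.0680/43 = 0.00158 and 0.0294/29 = 0.00101, ratio 0.64 against 0.43 uncorrected, so the bias is reduced but not removed.

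**The case against.** The strongest reply is that this is loose wording in one illustration. Aspiration pneumonia is introduced as an example beside death from all causes, the 50-day limit is not clearly attached to death, and the boundary can be run on whatever SAEs are recorded. That is fair, and it limits the point to this event. It does not remove it: the event is written into the rule, and the recording section cannot supply it as written.

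Second, bias is possible but not shown. The documents give no lag distribution, Section 9 prefers a visit within two days of referral, and equal lag leaves the ratio unbiased. All of this stands. A reader might infer that recruitment lag would trigger or block a stopping decision by itself. Step 2 does not support that: 3 standard errors is reached only with large differences in lag. A diluted or masked signal is likelier than a false alarm.

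Third, a reader might infer from Appendix 1, which lists SAEs only at weeks 12 and 26, that capture waits for those visits. It does not. Sections 13.3 to 13.5 require regular monitoring, enquiry during the hospital stay, review of hospital records for in-hospital events, and an SAE form within 24 hours of awareness. The gap lies before consent, not after it.

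Fourth, a person-time term in the final count model can be left to a statistical analysis plan, and the safety section's adjustment as per the primary analysis may absorb some calendar drift in lag. Agreed: its absence is not the fault here. No such adjustment is stated for the DSMC comparison, and none restores unrecorded events.

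**Conclusion.** The Protocol puts an interim safety event on an injury clock and its recording on a consent clock, with up to 42 days between them and no provision for looking back. The unobserved part of the 50-day window is 4% at day 2, 56% at day 28 and 84% at day 42. Those shares need only the Protocol's own limits.

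The certain consequence, whenever consent comes after injury, is lost events and a weaker safety signal. Bias between conditions is conditional: it needs lag to differ by site or period, which the design allows and the documents do not establish. The ratios and z values rest on assumed risks, hazards, lags and an equal split of 312, and serve as illustrations only.

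Starting SAE recording at consent is a reasonable choice. The fault is pairing it with an event counted from injury. The primary efficacy analysis is not affected. The point should be corrected because it concerns a stopping boundary and the repair is cheap.

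**What to change.** Reconcile Section 13.3, Section 16.4.2 (items 1 and 5), Sections 7.2, 9 and 10.2.1, and Appendix 1, so that the event and its recording share one clock and a single latest consent day applies throughout.

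- **Simplest:** define the interim event from consent and have the DSMC compare rates per observed person-time between conditions. Use log observed person-time as an offset in the count model of Section 16.4.2, item 1. Because an offset corrects fully only under a constant hazard (Step 4), also report days from injury to consent by condition and consider it as a covariate. The cost is a few lines of wording and a narrower event definition.
- **Alternative:** for every consented participant in both conditions, record SAEs from the index admission, abstracted from the hospital record at enrolment, and keep the injury-based window. State that events fatal before consent remain unobserved, so some dependence on lag is left. The cost is slight extra abstraction work.

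The existing audit in Section 10.4 is a weaker vehicle for the second option. It runs at six-month intervals, which is slow for interim monitoring, and it would still include only people who survived to consent.

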### **13.4 Recording of AEs and SAEs**

When an AE/SAE occurs in hospital, it is the responsibility of the investigator to review all documentation (e.g. hospital progress notes, laboratory, and diagnostic reports) relative to the event. The investigator will notify the Project Manager and will record all relevant information regarding an AE/SAE in to the CRF. There may be instances when copies of medical records for certain cases are requested. In this instance, all participant identifiers will be blinded on the copies of the medical records prior to submission to the Sponsor.

For each reportable event, start and stop dates, action taken, outcome, intensity and relationship to study treatment (causality) will be documented. If an AE changes in frequency or intensity during a study, a new entry of the event must be made in the eCRF.

The investigator will attempt to establish a diagnosis of the event based on signs, symptoms, and/or other clinical information. In the absence of a diagnosis, the individual signs/symptoms should be documented.

All details of any treatments initiated due to the adverse event should be recorded in the participant's notes and the eCRF.

### 13.5 Prompt Reporting of SAEs to the Sponsor

Once an investigator or assessor becomes aware that an SAE has occurred in a study participant, he/she will immediately notify the sponsor by contacting the Project Manager via telephone. The SAE form must be completed as thoroughly as possible with all available details of the event, signed by the investigator (or appropriately qualified designee), and sent to the Project Manager within 24 hours of first becoming aware of the event.

If the investigator does not have all information regarding an SAE, ***he/she will not wait to receive additional information before notifying the Project Manager*** of the event and completing the form. The form will be updated when additional information is received.

The blinded assessor will always provide an assessment of causality at the time of the initial report as described in Section 13.6.2, "Assessment of Causality".

In accordance with local IEC requirements, the investigator must also notify their Ethics Committee of any SAEs according to the guidelines of the Ethics Committee.

Those adverse events that are **CAUSALLY** related to the study treatment, **AND** that are both **SERIOUS** and **UNEXPECTED** – see section 9.8.3) are subject to expedited reporting to the independent Data Safety Monitoring Committee (DSMC).

The investigator, and others responsible for participant care, should institute any supplementary investigations of serious adverse events based on their clinical judgement of the likely causative factors. This may include seeking further opinion from a specialist in the field of the adverse event. If a participant dies, any post-mortem findings may be requested by the Sponsor.

### 13.6 Evaluating AEs and SAEs

#### 13.6.1 Assessment of Intensity

The investigator will make an assessment of intensity for each AE and SAE reported during the study. The assessment will be based on the investigator's clinical judgement and assigned to one of the following categories:

**Mild:** An event that is easily tolerated by the subject, causing minimal discomfort and not interfering with everyday activities.

**Moderate:** An event that is sufficiently discomforting to interfere with normal everyday activities.

**Severe:** An event which is incapacitating and prevents normal everyday activities.

An AE that is assessed as severe should not be confused with an SAE. Severity is a category utilised for rating the intensity of an event; and both AEs and SAEs

can be assessed as severe. An event is defined as “serious” when it meets one of the pre-defined outcomes as described in Section 13.2 “Definition of an SAE”.

### 13.6.2 Assessment of Causality

The blinded assessor is obligated to assess the relationship between study treatment and the occurrence of each AE/SAE. The blinded assessor will use clinical judgment to determine the relationship. Alternative causes, such as natural history of the underlying diseases, concomitant therapy, other risk factors, and the temporal relationship of the event to the treatment period will be considered.

The causal relationship to the study treatment assessed by the blinded assessor should be assessed using the following classifications:

- Not Related** In the Assessors opinion, there is not a causal relationship between the study product and the adverse event.
- Unlikely** The temporal association between the adverse event and study treatment is such that the study treatment is not likely to have any reasonable association with the adverse event.
- Possible** The adverse event could have been caused by the study treatment.
- Probable** The adverse event follows a reasonable temporal sequence from the time of study treatment, abates upon discontinuation of treatment and cannot be reasonably explained by the known characteristics of the study participant’s clinical state.
- Definitely** The adverse event follows a reasonable temporal sequence from the time of study treatment start or reappears when study treatment is reintroduced.

